**Data sources:**

This study is planned as analysis of routinely collected health data in five secondary automated electronic data sources in four countries (Denmark, Norway, Spain, and the United Kingdom [UK]). The data access providers (DAPs) are selected based on availability of the required routinely collected data, including information on vaccine brand and frequency of data updates, in cooperation with the established VAC4EU association. As feasible, linkage to medical records is planned for case confirmation and if applicable, collection of data on risk factors and outcomes not available in structured data. Local laws and regulation will apply for case validation and data collection.

**Study size:**

Considering the type of investigation, a traditional sample size calculation cannot be provided. Given that the number of cases is expected to be limited, and the number of possible risk factors for post-vaccine myocarditis (including demographic characteristics, lifestyle factors, medical history, and vaccination characteristics) under investigation, all individuals that meet the criteria for the outcome will be selected as cases, and four times as many controls will be sampled to improve statistical efficiency. The number of myocarditis cases will drive the number of risk factors that can be investigated with adequate power in this study. The nature of this study will therefore be observational and exploratory.

Derived from literature, it is assumed that the incidence of myocarditis and pericarditis is approximately 0.4-4.0 per 100,000 individuals. Based on the inclusion of subjects of the DAPs for Denmark, Norway, Spain and UK, we expected a total size of 27-270 cases for each outcome separately. Based on preliminary results, however, the expectation was adjusted to 40-160 cases of myocarditis and 100-280 cases of pericarditis for the cohort design per DAP. For the Moderna vaccination-exposed case-cohort design, a study size of 100-400 is expected for myocarditis, and 250-700 for pericarditis per DAP.

**Data analysis:**

In the Moderna vaccination-exposed case-cohort design, all cases of myocarditis, pericarditis and the control population will be described with respect to demographic characteristics, lifestyle factors or proxy variables of lifestyle factors (depending on the availability in each database), medical history and vaccination history. The control group will be a sample of the cohort of Moderna vaccination-exposed individuals aligned with the distribution to cases based on the month and year of documented Moderna vaccination targeting SARS-CoV-2 receipt.

A predictive modelling approach will be used to identify risk factors for development of myocarditis or pericarditis within the Moderna vaccination-exposed population.

In the cohort design, all cases of myocarditis and pericarditis will be described in terms of demographic characteristics, lifestyle factors or proxy variables of lifestyle factors (depending on

the availability in each database), medical history and vaccination characteristics. Clinical course of the myocarditis/pericarditis event will be described for these cases. To identify differences in risk factors for myocarditis/pericarditis with a severe clinical course or long-term sequelae, the different variables of demographic, lifestyle factors, medical history and vaccination characteristics at the time of Moderna vaccination targeting SARS-CoV-2 will be assessed. Outcomes and identified follow-up care will also be characterized. If sequelae or unusually severe cases are able to be identified, cases with and without sequelae will be compared within the exposed and unexposed groups.

Descriptive statistics and statistical model results will be presented, and details of these will be provided in the SAP.

As primary analysis, the case-cohort and the cohort analyses will be performed for all Moderna vaccinations targeting SARS-CoV-2 combined. If feasible, the case-cohort and cohort analyses will also be performed separately for different variants of the Moderna vaccine (e.g., Spikevax and the Spikevax bivalent Original/Omicron BA.1 and Original/Omicron BA.4/BA.5 vaccines separately) as subgroup analyses.

### **Milestones:**

Data collection will start March 2023 (pending timelines for endorsement of the protocol) and continue through the second quarter of 2024. Upon data transformation by DAPs, the final analytical dataset will be available 31 August 2024 with a final study report planned by June 2025. Interim analysis reports are planned every twelve months. Progress reports are planned every six months.

## **5. Amendments and updates**

Number	Date	Section of study protocol	Amendment or update	Reason
1.0	26-APR-22	NA – Initial version	NA – Initial version	NA – Initial version
2.0	11-AUG-22	Section 1,4,5,6,7,8,9, and 13	1: Table of Contents updated 4: Abstract updated to reflect all protocol updates 5: Amendments and Updates: updated to summarize changes	EMA feedback obtained on initial version

Number	Date	Section of study protocol	Amendment or update	Reason
			
6: Milestones: updated to reflect current timelines
 
7: Rationale and Background: Updated in line with EMA feedback
 
8: Research Question and Objectives: updated in line with EMA feedback
 
9: Research Methods: updated in line with EMA feedback, defined study population, end of data collection, calculation of case estimation, description of analytical principles and limitations of the research method
 
13: References: updated reference list
	
2.1	29-AUG-22	Throughout	The exposure of interest has been revised from the original strain vaccine (elasomeran) to also include the omicron-containing bivalent vaccine (imelasomeran). Subgroup analyses have been added to consider each exposure separately as data allow.	EMA request
3.0	25-JAN-23	Title, and section 3,4,6,7, 9 and 13	
Title: adjusted to reflect the incorporation of different variants of the Moderna vaccine targeting SARS-CoV-2
 
4: Abstract adjusted to reflect the inclusion variants of the
	EMA feedback obtained on Version 2.1

Number	Date	Section of study protocol	Amendment or update	Reason
			Moderna vaccine targeting SARS-CoV-2 in the study.  6: Date of study interim report 1 changed  7: Rationale and background: Updated in line with EMA feedback  9: Research methods: Updated in line with EMA feedback and to incorporate the inclusion of different variants of the Moderna vaccine targeting SARS-CoV-2.  13: Updated reference list	
		Throughout	Minor administrative and cosmetic updates have been incorporated throughout the document for clarity.  Moreover, several changes to the study methods were incorporated. These changes are all minor and are not expected to lead to changes in project outcomes. For instance: 
 
- Case validation will be based on criteria according to the Brighton Collaboration Case Definition instead of the CDC case definition.
 
- Inclusion criteria for the cohort design have been redefined. That is, individuals are now also
 
	Other changes not requested by EMA. The decision to use criteria according to the Brighton Collaboration Case Definition instead of the CDC case definition was made following VAC4EU's preference for the former of the two.

Number	Date	Section of study protocol	Amendment or update	Reason
			
included if they received a non-Moderna vaccination targeting SARS-CoV-2 within the 30 days prior to myocarditis or pericarditis onset, as long as they also received a Moderna vaccination in the same time window and meet the other inclusion criteria.
 
 
- For the main analyses, a Cox regression methodology will be used instead of a logistic regression.
 
- Handling of missing data is now done in a different manner.
 
	
3.1	22-MAY-23	9.2.2, 9.2.3 Inclusion and exclusion criteria	
 
• Updated language to clarify inclusion and exclusion criteria using text suggested by the EMA.
 
	EMA feedback obtained on Version 3.0
		9.1 Study design	
 
• Added text to clarify end of study period
 
	Other changes not requested by EMA
		Throughout	
 
• Updated contact list details.
 
	Other changes not requested by EMA

Number	Date	Section of study protocol	Amendment or update	Reason
4.0	24-JAN-24	Throughout	
 
Minor cosmetic and textual updates have been incorporated for clarity
 
	Update for clarification
		9.2.1 Study period	
 
Updated text to clarify the definition of the End of Data collection
 
	Update for clarification
		9.2.2 Inclusion criteria; 9.3.2 Outcomes	
 
Updated to reflect a novel approach for case validation in the cohort study design
 
	Reducing the total number of cases to be adjudicated due to feasibility reasons.
		9.5 Study size	
 
Updated study size calculation to reflect new insights and preliminary results
 
	EMA feedback received on version 3.1
		9.7.2 Main analyses	
 
For the case-cohort main analyses, conditional logistic regression will be performed instead of Cox analyses
 
	In response to feedback from US FDA on version 3.1
		9.9 Limitations of the research methods	
 
Added text to clarify potential limitations related to the case validation and the sampling of cases for validation
 
	Updated in line with the novel approach for case validation proposed in Section 9.2.2

## 6. Milestones

Milestone	Planned date*

Protocol Final	24 January 2024
Registration in the EU PAS register	Following EMA endorsement of the study protocol
Start of data collection	31 March 2023
End of data collection	31 August 2024
Study interim report 1 (written progress report, no data analysis)	30 August 2022
Study interim report 2 (written progress report, no data analysis)	31 January 2023
Study interim report 3 (written progress report, no analysis)	30 June 2023
Study interim report 4 (interim analysis 1, including preliminary analysis on study objectives)	31 January 2024
Study interim report 5 (written progress report, no analysis)	30 June 2024
Study interim report 6 (interim analysis 2, including preliminary analysis on study objectives)	31 January 2025
Final report of study results	30 June 2025

\* Subject to data queues by data custodians; refer to [Section 12](#) “Plans for disseminating and communicating study results” for planned contents of the interim reports

## 7. Rationale and background

The severe acute respiratory syndrome coronavirus 2 (SARS-CoV-2) causes coronavirus disease 2019 (COVID-19) and has led to a global pandemic. A mass vaccination campaign has been implemented in Europe.

Rare cases of cardiac inflammation, i.e., myocarditis and pericarditis, have been observed following vaccination with mRNA vaccines targeting SARS-CoV-2, including the Moderna vaccine.

Most of these cases have occurred within 14 days following vaccination, more often after the second dose and in younger men.

Myocarditis is an inflammatory disease of the myocardium (heart muscle) and may be due to any one of numerous etiologies, including infectious pathogens, toxins, drugs, and autoimmune disorders. The condition may resolve spontaneously or with supportive care, but it may also be associated with heart failure, dilated cardiomyopathy, cardiogenic shock, and arrhythmias. The most common etiology of myocarditis, especially among younger people, is viral infection including SARS-CoV-2. Younger men are typically at higher risk. Pericarditis is an inflammation of the pericardial layers and is the most common form of pericardial disease. Causes may be infectious or non-infectious, but most cases remain idiopathic. Similar to myocarditis the clinical course is typically mild with most cases making a full recovery.

The EU Risk Management Plan (RMP) for Moderna vaccines targeting SARS-CoV-2 lists myocarditis and pericarditis as important identified risks. Missing information includes use in pregnancy and while breastfeeding (to be addressed in a separate protocol), long-term safety, use in immunocompromised subjects, interaction with other vaccines, use in frail subjects with unstable health conditions and chronic co-morbidities (e.g., chronic obstructive pulmonary disease, diabetes, chronic neurological, disease, cardiovascular disorders), and use in subjects with autoimmune or inflammatory disorders.

On 09 July 2021, the EMA's Pharmacovigilance Risk Assessment Committee (PRAC) concluded that myocarditis can occur in very rare cases following vaccination with the two current mRNA vaccines targeting SARS-CoV-2. This conclusion was reached after an in-depth review of 145 cases of myocarditis in the European Economic Area (EEA) among people who received Comirnaty and 19 cases among people who received the Moderna vaccine. PRAC also reviewed reports of 138 cases of pericarditis following the use of Comirnaty and 19 cases following the use of the Moderna vaccine. The PRAC concluded that the cases primarily occurred within 14 days after vaccination, more frequently after the second dose, with young age, and male sex identified as potential risk factor for occurrence. Among those with myocarditis, advanced age and concomitant diseases were risk factors for subsequent mortality. As PRAC qualified this adverse event of special interest (AESI) as 'very rare', an updated product information will list myocarditis as side effects with very rare frequency and health care professionals are advised that the cases may need specialist care. Although vaccine trials are usually large, they may not detect rare adverse events. In addition, there is a high safety standard applied to a preventive agent administered to individuals in their usual state of health.

Population-based descriptive studies have addressed the occurrence of myocarditis after mRNA-based vaccination targeting SARS-CoV-2. In Denmark, 21 persons among a half million individuals who received the Moderna vaccination targeting SARS-CoV-2 developed myopericarditis within 28 days from vaccination date. The Moderna vaccination targeting SARS-CoV-2 was associated with a significantly increased risk compared to unvaccinated individuals. In another study passive surveillance reporting in the US showed that rates of myocarditis were highest after the second

vaccination dose of mRNA-based vaccines. In the latter study 490 myocarditis cases following Moderna vaccination targeting SARS-CoV-2 were reported to the Vaccine Adverse Event Reporting System. As both studies merely focused on short-term follow-up and myocarditis is a rare adverse event, larger international studies with longer follow-up time are needed.

The association between mRNA-based vaccination targeting SARS-CoV-2 and the increased risk for the development of myocarditis or pericarditis has already been well established in previous studies. However, it is important to further assess using other characteristics which individuals who received mRNA-based vaccinations targeting SARS-CoV-2 are at the highest risk of developing myocarditis.

Although most cases of vaccine-associated myocarditis and pericarditis have been described as mild, additional data are needed to characterize the natural history and long-term outcomes of these events and characterize risk factors for both occurrence and severity.

## **8. Research question and objectives**

The overarching goal of this study is to describe the risk factors, clinical course and outcomes for myocarditis and pericarditis temporally associated with Moderna vaccination targeting SARS-CoV-2.

We want to investigate the clinical course in terms of morbidity and to identify the relevant prognostic factors using the following study objectives.

### **8.1 Primary objectives**

1. To identify possible risk factors for myocarditis and pericarditis following Moderna vaccination targeting SARS-CoV-2, including demographic characteristics, medical history, and vaccination characteristics.
2. To characterize the clinical course of myocarditis and pericarditis of varying origin, including myocarditis and pericarditis associated with Moderna vaccination targeting SARS-CoV-2, and myocarditis or pericarditis not associated with vaccinations targeting SARS-CoV-2, and to identify prognostic factors in the course of myocarditis and pericarditis

### **8.2 Secondary objectives**

1. To identify whether there are differences in the clinical course and risk factors between myocarditis and pericarditis associated with Moderna vaccination targeting SARS-CoV-2, and myocarditis and pericarditis not associated with vaccinations targeting SARS-CoV-2
2. If severe cases or cases with sequelae are identified, to identify risk factors for severe myocarditis and pericarditis associated with Moderna vaccination targeting SARS-CoV-2

Confirmed cases are those that meet clinical adjudication criteria for myocarditis or pericarditis based on review of clinical data. The adjudication process will use a structured questionnaire that adapts the Brighton Collaboration Case Definition to those elements available in the clinical data available for validation, and will be both informed by expert cardiologist advice and documented in a separate medical record adjudication plan prior to the initiation of case review. Within the cohort study, not all cases undergo validation. All cases following vaccination are included in the validation process, as well as a 1:1 age and sex matched sample of cases not following vaccination.

Final definitions of the level of data details, study variables and detailed descriptions of analyses methods and presentations will be provided in the Statistical Analysis Plan (SAP), which will be developed with clinical and statistical input from all relevant parties involved and the participating database experts.

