**Population:**

For the case-cohort design, the cohort is the group of individuals with at least one dose of a Moderna vaccination targeting SARS-CoV-2. Inclusion criteria are at least one year of enrolment in the applicable database prior to the index vaccine dose and without myocarditis events within 6 months prior to receiving a Moderna vaccination targeting SARS-CoV-2. Cases are individuals meeting the criteria of myocarditis or pericarditis. Moreover, cases should be able to meet the adjudication criteria according to the Brighton Collaboration Case Definition for possible, probable, or definite myocarditis or pericarditis.

For the cohort design, individuals meeting the criteria of myocarditis or pericarditis, with at least one year of enrolment in the applicable database prior to the index myocarditis or pericarditis event will be included. Cases of myocarditis and pericarditis will be excluded if these individuals have no record of a Moderna vaccine targeting SARS-CoV-2 but a record of another vaccine targeting SARS-CoV-2 within 30 days prior to the onset of myocarditis or pericarditis. Within the cohort design, all cases following vaccination are adjudicated according to the Brighton Collaboration Case Definition. A 1:1 matched sample of the cases not following vaccination matched based on sex and age will also be adjudicated. Only cases that meet the adjudication criteria for possible, probable, or definite myocarditis or pericarditis are included.

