### 9.2.2 Inclusion criteria

For the Moderna vaccination targeting SARS-CoV-2-exposed case-cohort design, a cohort will first be defined including individuals of all ages with (1) at least one dose of Moderna vaccination targeting SARS-CoV-2 administered during the study period, (2) at least one year of enrolment in the applicable database prior to the index vaccine dose to allow for ascertainment of baseline covariables and potential risk factors, and (3) no myocarditis or pericarditis events within 6 months prior to Moderna vaccination receipt. Myocarditis and pericarditis cases are defined when adjudication criteria according to the Brighton Collaboration Case Definition for possible, probable or definite myocarditis or pericarditis is fulfilled. Cases and controls are defined as mentioned in [Section 9.1.1](#).

In the cohort design, all cases following vaccination, and only a sample of cases not following vaccination will undergo adjudication. In the analyses, individuals will be included if they: (1) have been adjudicated and meet the adjudication criteria according to the Brighton Collaboration Case Definition for possible, probable or definite myocarditis or pericarditis, and (2) have at least one year of enrolment in the applicable database prior to the index myocarditis or pericarditis event to allow for ascertainment of baseline covariates and potential risk factors.

For both the case-cohort as the cohort design, individuals with administrative codes for myocarditis or pericarditis will be identified in each data source. Following this initial screening, selected cases will be confirmed based on review of clinical data (based on criteria according to the Brighton Collaboration). The selection will include all cases of myocarditis and pericarditis following Moderna vaccination targeting SARS-CoV-2, as well as an age- and sex- matched sub-sample of other cases.

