### Cohort analysis

To identify differences in clinical course (Primary objective 2) and differences in risk factors (Secondary objective 1) for vaccine associated myocarditis/pericarditis and vaccine unrelated myocarditis/pericarditis, cases in the cohort analysis will be compared based on vaccination status. Outcomes and identified follow-up care will also be characterized, where feasible. If sequelae or unusually severe cases are identified, cases with and without sequelae will be compared.

Standard descriptive statistics (see [Section 9.7](#)) will be used to characterise clinical course, outcomes, and long-term outcomes following the initial myocarditis/pericarditis episode. Cox regression analysis will be utilized to compare the presence of sequelae following myocarditis/pericarditis (e.g., death, subsequent cardiovascular events, cardiac hospitalizations) between recent Moderna vaccination targeting SARS-CoV-2-exposed and unexposed cases as feasible.

If myocarditis and pericarditis cases with severe presentation or long-term sequelae are identified, a similar modelling approach for the cohort design will be applied to explore applicable risk factors as feasible (Secondary objective 2). Candidate risk factors will be selected using a two-step variable selection method: starting with a univariate approach for the selection of relevant variables, and followed by a stepwise backward variable selection approach.

The analysis will be performed per DAP (i.e., models will be trained locally for each DAP), and results will be presented on DAP level. The parameter estimate, SE, and hazard ratio (HR) for each model parameter will be presented together with its 95% CI.

Further details on all analyses can be found in the SAP.

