and might make some (subgroup) analyses challenging regarding achieving adequately powered statistical analyses. Data availability may also limit our ability to address primary and secondary study objectives related to the identification of lifestyle factors as risk factors for the development of myocarditis/pericarditis. While the merits of investigating lifestyle factors as potential risk factors may be questioned when the data availability cannot be assured, we believe it is central to the research question to consider and rule out potential confounders whenever possible. Namely, we want to be able to determine the risk of myocarditis or pericarditis following vaccinations targeting SARS-CoV-2 over and above other common factors (e.g., age, smoking status). To this end, we will investigate as many lifestyle factors as feasible across all DAPs. Where not feasible (i.e., certain DAPs are missing a given lifestyle factor), analyses will include a smaller subset of variables and/or will only be done for those DAPs that have the requisite data available.

The sampling of cases (i.e., myocarditis or pericarditis not following vaccination) to be validated could pose a limitation in the characterization of the clinical course of cases not following vaccination. As most myocarditis and pericarditis cases following vaccination are expected to occur in young adults, age-matched non-vaccine related myocarditis/pericarditis cases will also mainly comprise of young adults. This may lead to an underrepresentation of non-vaccination related cases in older individuals in the cohort analysis. However, the sensitivity analysis including all cases, regardless of being validated or not, will provide information regarding the clinical course of non-vaccine related cases in possible underrepresented age groups.

There are a few other potential validity issues in this study. Selection bias is not expected to pose a threat to validity, as the routinely collected data are sufficiently representative of the background population. That is, the registries have full population coverage in Denmark and Norway, while the regional databases in Spain are representative with respect to background rates and demographic distributions of the underlying populations. Similarly, the CPRD is broadly representative of the UK population (see [Annex 3](#)).

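### The 1:1 age and sex matching of adjudicated comparison cases removes, by design, the age and sex contrast that secondary objective 1 asks for in the cohort set

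*Protocol*

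**What the plan says.** Section 8.2 sets secondary objective 1: "To identify whether there are differences in the clinical course and risk factors between myocarditis and pericarditis associated with Moderna vaccination targeting SARS-CoV-2" and cases not associated with such vaccination. Section 9.1 adds that risk profiles, as well as clinical course, are compared between the two groups. Section 9.7.2 (Cohort analysis) assigns the differences in risk factors to this objective and says that "cases in the cohort analysis will be compared based on vaccination status". The abstract gives age and sex as examples of the demographic risk factors to be explored, and Section 9.3.3 lists both as key covariables.

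Section 9.2.2 limits the analysed cases to those who "have been adjudicated and meet the adjudication criteria according to the Brighton Collaboration Case Definition for possible, probable or definite myocarditis or pericarditis". The abstract (Population) agrees: "Only cases that meet the adjudication criteria for possible, probable, or definite myocarditis or pericarditis are included". On the comparison cases it says: "A 1:1 matched sample of the cases not following vaccination matched based on sex and age will also be adjudicated". Section 8.2 repeats the rule: "All cases following vaccination are included in the validation process, as well as a 1:1 age and sex matched sample of cases not following vaccination". Under Section 9.2.3, coded cases left unreviewed because of the sampling are described but stay out of the primary analyses.

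Section 9.9 discusses the sampling as a limit on characterising clinical course: "This may lead to an underrepresentation of non-vaccination related cases in older individuals in the cohort analysis". It points to a sensitivity analysis of all cases, validated or not, again for clinical course. Section 9.7.5 lists that analysis among those that may be done, as feasible.

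**The concern.** A factor used for matching cannot be compared between the matched groups. The plan names age and sex as risk factors, asks for differences in risk factors between the two kinds of case, and then equalises age and sex when it selects the comparison cases. A table of the cohort by vaccination status would show little or no difference in either. A reader could take that for a finding when it is produced by the sampling. Factors that rise with age, such as many of the listed comorbidities, are drawn together as well.

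Sections 7 and 9.9 themselves treat young age and male sex as the leading features of vaccine-related cases, so these are the factors on which the contrast would be of most interest. A lesser effect falls on primary objective 2. Section 7 notes: "Among those with myocarditis, advanced age and concomitant diseases were risk factors for subsequent mortality". A set matched to mainly young cases offers a narrower age range in which to study age as a prognostic factor.

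**Working it through.** **1. Is the matched set really the analysed set?** Section 9.5 expects 20–80 vaccine-exposed myocarditis cases and 50–140 pericarditis cases per data access provider (DAP). With 1:1 matching the cohort is twice that:

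- myocarditis: 2 × 20 = 40 and 2 × 80 = 160
- pericarditis: 2 × 50 = 100 and 2 × 140 = 280

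These are exactly the cohort sizes per DAP in the abstract (40–160 and 100–280), so the study size was built on the matched set. One labelling conflict needs care. The abstract calls 100–400 and 250–700 case-cohort sizes per DAP, whereas Section 9.5 gives them as totals over five DAPs (5 × 20 to 5 × 80; 5 × 50 to 5 × 140). Doubling 100–400 would give 200–800, not 40–160, so the cohort figures fit Section 9.5.

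**2. What matching does.** Let v be the male share of the vaccine-related cases. With exact 1:1 matching the comparison cases have male share v too, so the difference is v − v = 0 and the odds ratio is 1, whatever the share u among all other cases. The same holds for age, to the width of the matching bands. For a factor that depends on age, the crude group difference has one part due to different age distributions and one part present at a given age. Matching removes the former and keeps the latter.

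**3. Size, on assumed shares.** The protocol gives no sex split, so v and u are assumptions.

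Odds ratio = [v/(1−v)] / [u/(1−u)]. For example, (0.80/0.20)/(0.60/0.40) = 4/1.5 = 2.67.

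Power of an unmatched comparison with n per group, two-sided 5%, with m = (v+u)/2: Φ{[|v−u| − 1.96√(2m(1−m)/n)] / √[(v(1−v)+u(1−u))/n]}. For v = 0.80, u = 0.60, n = 80: (0.200 − 1.96 × 0.0725)/0.0707 = 0.82, so power is 0.79.

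| v | u | Unmatched OR | Power, n = 20 | Power, n = 80 | Matched OR before adjudication |
|---|---|---|---|---|---|
| 0.70 | 0.60 | 1.56 | 0.10 | 0.26 | 1 |
| 0.80 | 0.60 | 2.67 | 0.28 | 0.79 | 1 |
| 0.85 | 0.55 | 4.64 | 0.55 | 0.99 | 1 |

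The n values are the ends of the expected myocarditis range per DAP. An all-cases comparison would normally have more than n comparison cases; the protocol does not give that number.

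**4. After adjudication.** Matching precedes adjudication, so pairs can break. In a simulation with an assumed 80% confirmation in both groups, unrelated to sex (4,000 runs per setting), the mean difference in male share stayed within 0.002 of zero and a 5% test rejected in at most 0.1% of runs. If confirmation did vary with age, sex or vaccination status, any imbalance would reflect confirmation and not risk.

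**5. Does the plan recover the contrast elsewhere?** Section 9.9 does not mention risk factors when it discusses the sampling. The all-cases analysis of Section 9.7.5 is unmatched and could show the contrast, but it is optional and not tied to this objective. The description of unsampled cases in Section 9.2.3 is firm, but is not framed as a comparison by vaccination status. The case-cohort answers a different question: cases against other vaccine recipients.

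**The case against.** Several points on the other side stand. Matching is a sensible choice for comparing clinical course, and sampling for adjudication was a feasibility decision that the protocol discloses. The study is exploratory and the objective is secondary. Section 9.2.3 firmly promises a description of unsampled coded cases, so their age and sex can be reported.

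The wording can also be read another way. Table 1 lists only clinical outcomes as endpoints for secondary objective 1, and the abstract's data analysis text speaks of risk factors for a severe course. On that reading matching is ordinary confounding control. But Section 9.1 compares risk profiles between the groups, and Section 9.7.2 refers the risk-factor differences to vaccine-associated versus unrelated disease, so the plan at least invites the contrast it cannot deliver.

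A reader might infer that the study cannot assess age and sex as risk factors at all. The documents do not support that. Case-cohort controls are aligned only on month and year of vaccination (Section 9.1.1), and odds ratios are reported from that design under primary objective 1.

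A reader might also infer that older cases are gone from the cohort. They are not: every confirmed older post-vaccine case remains, the matched sample mirrors those ages, and Section 9.9 speaks of under-representation.

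**Conclusion.** The point holds for one contrast. In the primary cohort set, the difference in age and sex between vaccine-associated and other cases is removed by design before adjudication, and the difference in age-related factors is attenuated. No model fitted to that set alone can recover it without sampling weights. Age and sex remain estimable as risk factors in the case-cohort, and as prognostic factors within the matched set over a narrower age range.

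The odds ratios of 1.56 to 4.64 illustrate assumed shares and are not estimates. The matched value of 1 follows from the design, with three provisos: every case finds an exact match; confirmation does not vary with age, sex or vaccination status; and the groups compared are the groups matched. On the last, Section 8.2 gives no time window for a case following vaccination, while the Cox comparison in Section 9.7.2 is of recently exposed with unexposed cases, so an odds ratio of exactly 1 should not be promised.

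Nor should the unmatched odds ratio be read as a pure risk contrast. Without denominators, a comparison of cases with cases also reflects who received the vaccine. No figure for lost severe events can be given from the documents.

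**What to change.** Keep the matched adjudicated set for the clinical-course comparison. In Section 9.7.2:

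1. State that age and sex are not compared between the vaccination groups in the matched set.
2. For age, sex and age-related factors under secondary objective 1, commit to an unmatched comparison, not one that may be done. Use either all eligible code-identified cases, or the adjudicated non-vaccine cases weighted by the inverse of their age-by-sex sampling fraction.
3. Report it beside the matched result, with adjudication confirmation rates by age, sex and vaccination status.

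Section 9.9 should add that the sampling limits the risk-factor comparison as well as clinical course.

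No further record review is needed. Sections 9.2.2 and 9.2.3 already have the coded cases identified and described; for weighting, each DAP must record its sampling fractions, which the protocol does not mention. Each route has a price. Unvalidated cases bring misclassification, possibly differential, since Section 9.9 warns of more diagnosis in young males, and their use needs a stated exception to the adjudication rule. Weighting keeps that rule, but weights may be unstable in thinly sampled older strata, and strata with nobody sampled cannot be represented.
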